### 3. INTRODUCTION

#### 3.1. Study Rationale

Visceral leishmaniasis (VL) is a parasitic disease caused by obligate intracellular protozoan parasites, particularly by the species *Leishmania donovani* and *Leishmania infantum/chagasi*. If left untreated, cases of VL are typically fatal. While therapies are available to treat the disease, none are ideal for use (due to toxicity, route of administration and cost) in resource poor settings where the disease is endemic. As such there is a real unmet medical need for new, short course oral drugs for the treatment of this disease.

The Phase 1 programme will comprise a First Time in Human (FTIH) study of single and repeat ascending doses in healthy participants, incorporating a food effect component to investigate the influence of food on the pharmacokinetics (PK) of GSK3186899. The study will evaluate the safety, tolerability and PK profile of single and repeat ascending doses of GSK3186899. Results of this study are intended to be used to identify appropriate and well tolerated doses of GSK3186899 to be used in further studies. This study will be conducted at a single centre.

#### 3.2. Background

Visceral leishmaniasis is identified as a Neglected Tropical Disease by the World Health Organisation. As a systematic approach to drug discovery is relatively new in this neglected disease, GSK3186899 was identified through a phenotypic screening approach. Subsequently detailed mode of action studies utilising a variety of approaches, including genomics and chemical proteomics, have been undertaken which indicate that GSK3186899 acts principally by inhibiting the parasite complex of the cyclin dependent kinase; cdc 2 related kinase 12 (CRK12) with CYC9 as the definitive partner cyclin for CRK12.

More detailed information relating to non-clinical pharmacology, safety pharmacology, PK and metabolism, toxicology and other pre-clinical data can be found in the GSK3186899 Investigators Brochure [GlaxoSmithKline Document Number [2018N372131\\_00](#)].

#### 3.3. Benefit/Risk Assessment

There is no direct benefit to the participants taking part in this study.

To date, GSK3186899 has not been administered to human participants; therefore, no clinical data are available. This is the first single and repeat dose study proposed in human participants with GSK3186899. GlaxoSmithKline (GSK) is not aware of any compound targeting this pathway having previously been administered in humans.

The risk assessment of GSK3186899 is based on the pre-clinical studies conducted to date. Summaries of findings from these pre-clinical studies can be found in the Investigators Brochure (IB). Non-adverse vacuolation in the female rat adrenal glands

and ovaries was observed at the NOAEL and above, as a result some adrenal function monitoring has been added to this study. However, by observing the safety margin for renal findings of 3 to 5-fold below the female rat NOAEL (AUC: 434 µg.h/mL, Cmax: 46.2 µg/mL), this should reduce the risk of adrenal and ovary effects in humans. Details of the risks and the proposed strategy to mitigate/monitor these risks are detailed in Section 3.3.1.

The proposed risk assessment and management plan for the study has been developed in accordance with the tenets of European Medicines Agency (EMA) guideline on strategies to identify and mitigate risks for FTIH clinical trials with investigational medicinal products [European Medicines Evaluation Agency (EMEA)/ Committee for Medicinal Products for Human Use (CHMP)/SWP/28367/07]. GSK has assessed this study for any risks that may be posed to participants taking part. Only healthy male and female participants of non-child bearing potential will participate in this study.

In this study, safety will be monitored closely both by subjective reporting and by objective means, i.e. serial assessments of vital signs, clinical laboratory information and cardiac monitoring. The study will be run in a clinical unit with immediate access to hospital facilities for the treatment of medical emergencies. Participants will remain monitored in the clinic for the duration of each treatment period and will only be discharged from the unit at the end of each treatment period, if the investigator deems it safe to do so.

More detailed information about the known and expected benefits and risks and reasonably expected adverse events of GSK3186899 may be found in the IB [GlaxoSmithKline Document Number [2018N372131\\_00](#)].

### 3.3.1. Risk Assessment

Potential Risk of Clinical Significance	Summary of Data / Rationale for Risk	Mitigation Strategy
Investigational Medicinal Product (IMP) GSK3186899		
Kidney	
 
• Kidney tubule dilatation, which involved tubular epithelial cell loss, was noted in female rats given 400 mg/kg/day as spray dried dispersion (SDD), for 28 days (mean AUC 1290 µg.h/mL, mean Cmax 74.2 µg/mL on Day 28). This lesion is considered adverse in rats.
 
• These findings were associated with lower urine volume, with accompanying higher urine-specific gravity and lower urine pH, in females given 400 mg/kg/day.
 
• This lesion was not seen in 7-day rat studies nor in monkey toxicology studies of ≤21 days duration.
 
	
Inclusion/exclusion criteria:
 
 
• History of current or past significant renal diseases to be excluded.
 
• Screening eGFR (CKD-EPI) > 90 ml / min
 
• Urinary analysis at screening to be free of blood and protein. If trace protein is found, a repeat test will be performed within 24 hours
 
 
Monitoring:
 
 
• Serum Renal function and urinary analysis monitoring
 
• By observing the PK safety margin for renal findings of up to 3-fold (during the SAD part of the study) and up to 5-fold (during the MAD part of the study) for the total daily AUC and Cmax to be below the female rat NOAEL (AUC: 434 µg.h/mL, Cmax: 46.2 µg/mL).
 
 
Participant withdrawal
 
 
• New onset of any clinically significant and persistent haematuria / proteinuria (Spot Urine Protein Creatinine (UPC) ratio > 0.5) in the absence of another clinical explanation e.g. calculus / infection.
 

Potential Risk of Clinical Significance	Summary of Data / Rationale for Risk	Mitigation Strategy
		
 
Change in serum creatinine > 26 <math>\mu\text{mol/L}</math> (0.3 mg/dl) from baseline or > 50 % from baseline. If change in serum creatinine measures at > 26 <math>\mu\text{mol/L}</math> (0.3 mg/dl), repeat within 24 hours. If confirmed, the participant will be withdrawn. If a participant meets the withdrawal criteria for serum creatinine, then further investigations will be performed.
 
Hypophosphataemia (less than 0.8mmol/L). If confirmed, the participant will be withdrawn. If a participant meets the withdrawal criteria for hypophosphataemia, then further investigations will be performed.
 
 
Study Stopping criteria
 
 
The study will be temporarily halted if 2 or more participants across all study parts develop any of the above withdrawal criteria.
 

Stomach	
 
Stomach erosion/ulceration in the glandular region, was noted in female rats given 400 mg/kg/day (dose conc 40 mg/mL), as SDD, for 28 days (mean AUC 1290 <math>\mu\text{g.h/mL}</math>, mean <math>C_{\text{max}}</math> 74.2 <math>\mu\text{g/mL}</math> on Day 28). This lesion is considered adverse in rats.
 
Erosion/ulceration was not seen in NHPs given <math>\leq 150</math> mg/kg/day (dose conc 30 mg/mL), as SDD, for 21 days (AUC range across all doses 3.34 to
 
	
 
Contact time with stomach in humans are likely to be short (less than 2 hours) and concentrations considered in the human study are much lower than in the Rat study.
 
Participants with current or past history of clinically significant gastritis or gastroduodenal ulcers or regular NSAID use, will be excluded from the study based on medical history at screening.
 
Participants will be monitored for GI symptoms
 

Potential Risk of Clinical Significance	Summary of Data / Rationale for Risk	Mitigation Strategy
	
187 µg.h/mL on Day 21) nor in male rats given ≤1000 mg/kg/day (dose conc 100 mg/mL), as free base, for 7 days (AUC range across all doses 26.8 to 273 µg.h/mL on Day 7).
 
 
Localized erosion of the pyloric gastric mucosa was noted in the male monkey given 500 mg/kg/day (dose conc 100 mg/mL), as free base, for 7 days (mean AUC 896 µg.h/mL on Day 7) and focal ulceration of the mucosa at the gastro-duodenal junction and in the colon in the female given 150 mg/kg/day (dose con 30 mg/mL), as free base, for 7 days (mean AUC 613 µg.h/mL on Day 7). Erosion in the stomach and ulceration of the duodenum was noted in 1 female monkey given 500 mg/kg/day (dose con 100 mg/mL), as free base, for 14 days (mean AUC 545 µg.h/mL on Day 14).
 
Due to the localised nature and low incidence, these lesions are considered to be local, dose concentration-related, effects rather than due to systemic exposure.
 
	
reported as adverse events. Any reported symptoms which in the investigator's opinion raises a clinical suspicion of gastric erosion/ulcers, will be referred to a gastro enterology specialist for further management, and endoscopy (if required).

Adrenal gland	
 
Adrenal cortex vacuolation was noted in male and female rats given ≥100 mg/kg/day, as SDD, for 28 days (≥mean AUC 316 µg.h/mL, mean Cmax 44.0 µg/mL on Day 28).
 
Adrenal cortex vacuolar degeneration was noted in male rats given 1000 mg/kg/day, as free base,
 
	
 
These adrenal findings are considered not adverse and did not have any secondary effects in the rats. However, these findings were consistently observed in rats at all tested doses. The potential risk to healthy volunteers is expected to be low especially when administered as a single dose.
 

Potential Risk of Clinical Significance	Summary of Data / Rationale for Risk	Mitigation Strategy
	
for 7 days (mean AUC 204 µg.h/mL on Day 7).
 
 
• This test article-related, non-adverse finding correlated with increased adrenal weight following 28 days dosing in male rats given ≥100 mg/kg/day, as SDD, and female rats given ≥25 mg/kg/day, as SDD.
 
	
Therefore, no specific monitoring, other than standard clinical and laboratory parameters, will be implemented for healthy volunteers during SAD part of the study. However, for the MAD cohorts, adrenal function will be assessed prior to first dose and on completion of 10 days dosing. Also, by observing the safety margin for renal findings of up to 3-fold (during the SAD part of the study) and up to 5-fold (during the MAD part of the study) for the total daily AUC and <math>C_{max}</math> to be below the female rat NOAEL (AUC: 434 µg.h/mL, <math>C_{max}</math>: 46.2 µg/mL), should reduce the risk of adrenal and ovary effects in humans.
 
Exclusion criteria (Part B only):
 
 
• Participants with borderline adrenal glucocorticoid function (early morning serum cortisol < 420nmol/L) will only be included in the study if after an adrenocorticotropic hormone (ACTH) stimulation test, there is a rise in cortisol level from baseline of at least 250nmol/L
 
 
Monitoring:
 
 
• Participants will be monitored clinically for any symptoms of adrenal insufficiency, (nausea, vomiting, dizziness) and objective assessments (supine/standing BP). Depending on the investigators clinical judgement, a ACTH
 

Potential Risk of Clinical Significance	Summary of Data / Rationale for Risk	Mitigation Strategy
		
stimulation test may be done to exclude adrenal insufficiency.
 
Day 11 (Part B only):
 
 
• Early morning serum cortisol (+ ACTH stimulation test if levels < 420nmol/L) will be performed on all participants at Day 11. If during Day 11 early morning cortisol is < 420 nmol/L, volunteers will undergo a ACTH stimulation test the next day to rule out adrenal insufficiency. Participants with adrenal insufficiency will be withdrawn from the study, refer to Section 8.1.4.
 
 
Stopping criteria:
 
 
• A stopping criterion has been included if one or more volunteers in Part B develop adrenal insufficiency with clinical signs and symptoms.
 

Study Procedures		
Bile Sampling (Enterotest)	
As the swallowed capsule is attached to string, participants may experience a gagging sensation when the string is being withdrawn or may swallow the whole string. Sometimes streaks of blood can be seen on the nylon string after it is retrieved from the mouth, due to local irritation. Rarely, participants may be unable to swallow the capsule because of gagging or will vomit after doing so.
	
 
• Participants will be informed of these study procedure risks in the Information and Consent Form.
 
• To minimize the risk of swallowing the string, it will be securely taped to the side of the participants face.
 
• In the event of swallowing the whole string, no ill effects are anticipated as the nylon string will pass out from the body through the faeces.
 

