### Amendment 1 19-MAR-2019

**Overall Rationale for the Amendment:** To amend the protocol with required changes from the Medicines and Healthcare products Regulatory Agency, UK

Section # and Name	Description of Change	Brief Rationale
3.3.1 Risk Assessment & 6.2 Exclusion Criteria	The exclusion criterion on renal function has been amended to an age appropriate GFR (CKD-EPI) of $\leq 90$ (ml/min/1.73m  ).  In alignment with this change, the mitigation strategy in the risk assessment table has also been updated.	MHRA requested changes to exclusion criterion.
6.2 Exclusion Criteria	An additional criterion has been added to exclude participants with abnormally low blood pressure, as determined by the Principal Investigator.	MHRA requested changes to add an additional exclusion criterion.
7.3 Measure to Minimize Bias: Randomization and Blinding	Additional wording has been added to include information on general and emergency unblinding.	To correct an omission in the original protocol, as identified by the MHRA.
8.1.2 Dose Escalation / Study Progression Stopping Criteria	One criterion has been updated to remove reference to two or more participants on active treatment experiencing the same / medically similar AE. This wording has now been updated to:  “Two or more participants in the same cohort experience a severe non-serious adverse reaction (i.e. severe non-serious adverse events considered as, at least, possibly related to the IMP administration), independent of within or not within the same system-organ-class.”	MHRA requested changes to the stopping criterion.

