## 6.2. Exclusion Criteria

Participants are excluded from the study if any of the following criteria apply:

MEDICAL CONDITIONS

 
1. History or presence of or current cardiovascular, respiratory, hepatic, renal, gastrointestinal, endocrine, hematological, or neurological disorders capable of significantly altering the absorption, metabolism, or elimination of drugs; constituting a risk when taking the study treatment; or interfering with the interpretation of data.
 
2. Previous history of leishmaniasis
 
3. Alanine transaminase (ALT) <math>>1.5 \times</math> upper limit of normal (ULN).
 
4. Bilirubin <math>>1.5 \times</math> ULN (isolated bilirubin <math>>1.5 \times</math> ULN is acceptable if bilirubin is fractionated and direct bilirubin <math><35\%</math>).
 
5. Current or chronic history of liver disease, or known hepatic or biliary abnormalities (with the exception of Gilbert's syndrome or asymptomatic gallstones)
 
6. Current or past history of clinically significant gastritis or gastroduodenal ulcers or regular use of non-steroidal anti-inflammatory drugs (NSAID)
 
7. QTc <math>>450</math> msec
 
 
NOTES:
 
 
• The QTc is the QT interval corrected for heart rate according to Bazett's formula (QTcB), Fridericia's formula (QTcF), and/or another method, machine-read or manually over-read.
 
• The specific formula that will be used to determine eligibility and
 

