**DIAGNOSTIC ASSESSMENTS AND OTHER CRITERIA**

14. Subjects with renal function defined as Chronic Kidney Disease Epidemiology Collaboration (CKD-EPI) with an age appropriate GFR  $\leq 90$  (ml/min/1.73m^2).
15. Presence of Hepatitis B surface antigen (HBsAg) or Positive Hepatitis C antibody test result at screening.
16. Positive human immunodeficiency virus (HIV) antibody test.
17. Positive pre-study drug/alcohol screen.
18. Presence of clinically significant haematuria and/or proteinuria.

19. Carbon monoxide levels indicative of smoking or history or regular use of tobacco- or nicotine-containing products within 3 months prior to screening.
20. Abnormally low blood pressure as determined by the Principal Investigator
21. **Part A (Food Effect) Cohort 3 only:** Participant must have no dietary restrictions (e.g., lactose intolerance) or inability to eat an adapted standard meal (includes 35-40% fat content).
22. **Part A (Food Effect) Cohort 3 only:** History of gall bladder surgery or gall bladder removal, or history of an acute disease state (e.g. cholelithiasis) within 14 days prior to receiving the study treatment.
23. **Part B only:** Early morning cortisol < 420 nmol/L and inadequate response (rise of <250mmol/L from baseline) to ACTH stimulation test at Day -1.

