## 10.8. Appendix 2: Clinical Laboratory Tests

- The tests detailed in [Table 7](#) will be performed by The Doctor's laboratory.
- Protocol-specific requirements for inclusion or exclusion of participants are detailed in [Section 6](#) of the protocol.
- Additional tests may be performed at any time during the study as determined necessary by the investigator or required by local regulations.

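### Exclusion 18 is looser than the kidney entry screen in Section 3.3.1: confirmed urine blood or protein fails the stated safeguard but does not exclude unless judged clinically significant

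*Protocol*

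**What the plan says.** In Protocol Section 3.3.1, the kidney row of the risk table sets three entry conditions under its inclusion/exclusion heading: no significant renal disease, an eGFR above 90, and "Urinary analysis at screening to be free of blood and protein". The urine line has one qualification: "If trace protein is found, a repeat test will be performed within 24 hours". It makes no allowance for blood and has no clinical-significance filter.

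In Section 6.2, exclusion 18 reads "Presence of clinically significant haematuria and/or proteinuria". No threshold is attached there, and no inclusion criterion in Section 6.1 asks for a negative urinalysis.

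Two statements show which text governs. The opening of Section 6 disallows eligibility waivers. Appendix 2 (Section 10.8) says "Protocol-specific requirements for inclusion or exclusion of participants are detailed in" Section 6.

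Amendment 1 shows that the two sections are meant to agree. When the renal-function exclusion changed, the log records: "In alignment with this change, the mitigation strategy in the risk assessment table has also been updated".

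**The concern.** The risk table is where the protocol argues that a known hazard has been handled. Kidney tubule dilatation with loss of epithelial cells is described there as adverse in rats, and clean screening urine is one of three entry conditions offered against it. Section 3.3.3 then rests the benefit-risk conclusion partly on careful selection of participants. If the operative list admits people whom the risk table says are screened out, the safeguard described to the regulator and ethics committee is not the one applied.

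What is at stake is participant protection and a consistent eligibility rule in a first-in-human study that offers its participants no direct benefit. No power, error rate or effect estimate is involved.

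**Working it through.** No arithmetic applies, and the plan gives no figure to reproduce. The check is to apply both rules to the same volunteer.

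| Screening urine | Section 3.3.1 | Section 6.2, exclusion 18 |
|---|---|---|
| Negative | Passes | Passes |
| Trace protein, negative on repeat | Passes, by implication | Passes |
| Blood or protein confirmed, judged clinically significant | Fails | Excluded |
| Blood or protein confirmed, judged not clinically significant | Fails | Not excluded |

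The sections differ only in the last row, and there Section 6.2 is the looser. Section 3.3.1 does not say what follows if trace protein persists on repeat, but its plain rule is urine free of protein, so that case also belongs in the last two rows.

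The next question is whether any other text closes the last row.

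- **Inclusion 2 (Section 6.1).** This covers abnormalities that the criteria do not specifically list, and requires documented agreement that the finding is unlikely to add risk. Haematuria and proteinuria are named in exclusion 18, so it is arguable whether it applies. If it does, it allows enrolment on judgement; it does not exclude.
- **Schedule of Activities.** In Part A (Section 2.1), trace protein may be repeated within 24 hours and abnormal tests must be quantified. In Part B (Section 2.2), a repeat may be done, with no time limit and no quantification sentence. Neither attaches an eligibility consequence.
- **Appendix 2, Table 7.** Abnormal blood or protein leads to microscopy, and trace protein leads to a protein:creatinine ratio. No result of either is made an exclusion.
- **Section 9.1.5.** Its wording on clinically significant laboratory findings sets no threshold. It refers to an underlying disease, which healthy volunteers do not have.
- **Section 8.1.3.** A protein:creatinine ratio above 0.5 appears here, but for withdrawal on new, persistent findings, not for entry.

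None of these makes a confirmed positive an exclusion, so the last row stays open.

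**The case against.** The strongest reply is that the practical gap is small. A volunteer with a minor positive must still be judged healthy on laboratory tests. The work-up informs that judgement, and urinalysis is repeated on Day -1 in both parts. On study, KIM-1, NGAL and urinary albumin are measured, and Section 8.1.1 holds exposure 3-fold (single dose) or 5-fold (repeat dose) below the rat NOAEL. The urinary changes reported with the rat lesion were in volume, specific gravity and pH, not blood or protein. All of this stands. It limits the severity but does not reconcile the two sections.

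A second reply is that consistency alone does not say which section should move. In Amendment 1 the exclusion changed and the risk table followed, so adding a significance qualifier to Section 3.3.1 would also restore agreement. That is fair as logic. It would, however, withdraw a stated renal safeguard, and the documents give no reason for doing so.

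A reader might also infer two stronger points that the documents do not support.

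- **That the mismatch weakens the renal halt in Section 8.1.2, which needs two participants.** Section 8.1.3 uses the same clinical-significance term as exclusion 18. Anyone properly enrolled had no significant finding at screening, so a later significant and persistent one is new even if a minor dipstick positive came first. Creatinine and phosphate are separate withdrawal triggers.
- **That the urine line is the only one of the risk table's entry safeguards that does not match Section 6.2 exactly.** The gastric line, "Participants with current or past history of clinically significant gastritis or gastroduodenal ulcers or regular NSAID use, will be excluded", does carry over closely into exclusion 6. Others are reworded. Exclusion 1 begins "History or presence of or current cardiovascular, respiratory, hepatic, renal, gastrointestinal, endocrine, hematological, or neurological disorders" and then limits these to disorders that could alter drug handling, pose a risk or confuse the data. Exclusion 14 reads "Subjects with renal function defined as Chronic Kidney Disease Epidemiology Collaboration (CKD-EPI) with an age appropriate GFR", which adds an age qualifier, and its units differ from the risk table's. Exclusion 23 prints the cortisol rise in mmol/L where Section 3.3.1 has nmol/L. An exact count of matching safeguards would be a matter of classification.

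**Conclusion.** The inconsistency is real and lies in current text. Section 3.3.1 states an unqualified urine screen, while exclusion 18 applies a looser one with no threshold. Confirmed blood or protein judged not significant fails the first but is not excluded by the second.

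The screen is weakened, not absent. How many volunteers fall in the gap depends on the rate of confirmed dipstick positives and on how investigators judge them. The documents give neither, so no number can be offered. The conclusion assumes that Section 6 governs enrolment, as the protocol indicates, and that the urine line in Section 3.3.1 is meant as an entry condition, as its heading there says. It is a minor safety-consistency correction.

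**What to change.** Reword exclusion 18 to:

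*Blood or protein on screening urinalysis; trace protein is acceptable only if a repeat test within 24 hours is negative.*

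This follows Section 3.3.1 and settles what happens when trace protein persists. The note to inclusion 2 lets out-of-range laboratory values be repeated once at the investigator's discretion. If the sponsor wants one confirmatory repeat for blood (for example, away from menstruation, since Appendix 4 admits some premenopausal women) or for more than trace protein, that allowance should be written identically in Section 3.3.1 and exclusion 18. Adding it to one section only would create a new mismatch.

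The cost is amendment wording and any repeat urine tests allowed. Urinalysis is already scheduled at screening and Day -1, and the 28-day screening window leaves room for a repeat. The downside is possibly a few more screen failures, in a number the documents do not allow one to estimate.
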